Effect of Blueberry Supplementation on Alzheimer's Biomarkers

[name]

Duke University School of Medicine

10-29-2021

(Date of approval by Duke IRB)

NCT05172128

Scientific Rationale

Worldwide, some 40 million adults have Alzheimer's disease (AD) and several more million may be at elevated risk for AD by virtue of mild cognitive impairment (MCI) and/or silent buildup of cortical AD pathology (1). The failure of multiple therapeutic strategies in AD dementia highlights the need to develop risk reduction strategies in the earlier at risk stages.

Blood biomarkers have emerged to the forefront of AD research (2-13) spurred by the development of reliable ultra-sensitive "single-molecule array" assays with 100-1000-fold great sensitivity over traditional platforms (Table 1). Neurofilament light (NfL) is a marker of neuronal dysfunction whose elevation and rate of change are associated with cognitive decline and hippocampal atrophy (2-6). Studies in a variety of neurodegenerative disorders have also shown that elevated blood NfL levels reduce or normalize following therapy, sometimes within 10 weeks (2-6). A promising marker of glial activation is GFAP (glial fibrillary acidic protein). There is increased expression of GFAP in reactive glial cells surrounding amyloid plaques and blood GFAP is elevated in AD (7). Other blood markers (A β 42, A β 40, t-tau, p-tau) reflect neuropathology (8-15). For example, Schindler et al showed that plasma A β 42/A β 40 ratio predicts current and future brain amyloidosis (15). Park et al found plasma t-tau/ A β 42 predicted an AD pattern of neurofibrillary tangle deposition (8) as well as longitudinal changes in cerebral amyloid deposition, brain glucose metabolism, and hippocampal atrophy (8). Overall, the evidence makes a strong case for biomarker guided pilot trials in AD and MCI.

Practical, well tolerated and non-invasive lifestyle interventions are highly desirable for AD prevention in at-risk middle aged and older adults (16). Preclinical studies have reported that blueberry bioactives, such as anthocyanins, may impact many pathways involved in brain function or dementia risk - such as reduction of oxidative stress, improvement of inflammatory response, reversal of age-related decrements in cognition, increased cerebral blood flow, enhance microglial clearance of A β , inhibits aggregation of A β 1-42, suppresses microglial activation and protect against A β -induced neurotoxicity (reviewed in 16, 21-23). Despite this promising body of evidence, to our knowledge, no study has evaluated the effects of blueberry supplementation on pathological and neurodegeneration biomarkers in MCI.

Specific Objectives

The proposed pilot, open trial will examine the effect of treatment of blueberries on neuronal, glial, and pathology biomarkers in subjects with MCI. The blood markers to be measured are Neurofilament light (NfL), glial fibrillary acidic protein (GFAP), A β 42 and p-tau181 using an ultra-sensitive state-of-the-art digital immunoassay.

Primary Aim:

To generate pilot data on the effect of 3-months of blueberry consumption on blood biomarkers in MCI in order to calculate sample size estimates for future trials.

Hypothesis: Treatment with blueberry supplements will improve biomarker profiles in MCI.

Study Design

12-week open pilot trial. Following IRB approval all subjects will provide written informed consent. We will enroll 10 participants with MCI. The study duration is based upon the minimal time needed to expect a change in cognition and biomarkers. Eligible participants will be asked to abstain from berry fruits and other anthocyanin-rich foods during a 2-week washout period and for the duration of the trial.

Key Inclusion Criteria:

Age 55-85 years; both genders; stable medically; meets criteria for amnestic mild cognitive impairment (impaired delayed verbal recall, normal or near normal overall cognition and function). MCI diagnosis will be operationalized using criteria used widely (e.g. ADNI).

Key Exclusion Criteria:

Dementia , significant confounding active neurological/psychiatric disease; participation in an experimental investigational drug trial in the past 30 days; unwilling to restrict consumption of anthocyanin-rich foods; inability to complete cognitive testing (e.g. significant visual or hearing impairment); allergy or intolerance to blueberries; significant gastrointestinal disorders or surgery that influences digestion and absorption; history of frequent urinary tract or Clostridium difficile infections; presence of unstable, acutely symptomatic, or life-limiting illness.

After washout, participants will be receive blueberry supplement. Blood biomarkers (primary outcome) will be measured at zero and 12 weeks (as well as vital signs). Nutrient and berry intake function will be assessed at 0, 4, 8, and 12 weeks.

The blueberry dose of 36 grams per day in a split dose consumed with meals is based on 1) a 33% increase in dose over that previously used in a longer (6-month) trial; 2) delivering the most effective dose of blueberry bioactives; and 3) reduced likelihood of any gastrointestinal symptoms. Subjects will consume lyophilized blueberry powder, mixed with water (18 grams, equivalent to 3/4ths cup of blueberries) with 2 daily meals (36 g/d blueberry powder total; approx. 1.5 servings/d). Blueberry powders will be packaged in sealed single-serving packets (18 g/packet) to prevent exposure to light and moisture. Participants will be instructed to store them in home refrigerator to avoid degradation of blueberry bioactives. Participants will be instructed on storage, rehydration, dosing, and logging of supplement consumption as well as any inadvertent anthocyanin intake. Adherence will be measured during interim safety calls and return of empty packets.

Biomarker Assay

Venous blood will be collected at baseline and exit, and banked in -80 freezer for specified NfL, A β 42, p-tau and GFAP biomarker analyses. Participants will be counseled to consume a standardized flavonoid-free meal the night before the blood sample collection. Plasma NfL, A β 42, p-tau, GFAP are measured per Table 1.

Safety: AEs monitored via visits/phone calls (Table 2). SAEs will be reported to the IRB as appropriate. Study physician will oversee this. Possible risks are minor including anxiety or fatigue from testing and phlebotomy risks. The possible risks of blueberry consumption are minimal and well-studied. Participant information is kept confidential. Subjects will not be informed of their biomarker results due to their experimental nature and this will be pre-specified in the consent.

Data Analysis of Outcomes

As such this is a pilot study designed to generate power estimates for a larger future trial. Summary statistics will evaluate the change from baseline to endpoint in biomarker outcomes. Drop-out rates are expected to be low due to short duration and relatively benign intervention.

Possible Outcomes

The main possible outcomes in this study are a better understanding of the effects of blueberry on markers of neuronal dysfunction (reduction in neurofilament light levels), glial activation (reduction in GFAP) and plaque/tangle pathology (amyloid-beta, tau). This data will provide a strong scientific rationale for a larger controlled trial of blueberries in MCI or AD prevention.

Timetable

We plan to complete the study within 12 months from the receipt of funds/blueberry packets and IRB approval. We anticipate it will take about 30 days for staff training, purchase study materials such as biomarker assay kits, and finalize CRFs/database. We expect to finish enrolment by month 7 and complete the study by month 10. Biomarker assays and statistical analyses will be done by month 12. A final study report will be submitted.

Revised Budget

Budget and budget justification are presented in Table 2.

References

1. Alzheimer's Association. 2019. Alzheimer's Disease Facts and Figures. *Alzheimers Dement*. 2019;15(3):321-87.

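### Gastrointestinal symptoms enter the dose rationale but are not named in Safety, and with no symptom line in the home log, mild events between contacts may be under-recorded

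*Combined protocol and SAP*

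**What the plan says.** The design is a "12-week open pilot trial", and on size: "We will enroll 10 participants with MCI". Key Inclusion Criteria require that a participant "meets criteria for amnestic mild cognitive impairment (impaired delayed verbal recall"; the same criterion also asks for overall cognition and function at or close to normal.

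The dose paragraph, just before Biomarker Assay, gives three reasons for the regimen of 36 g/d, split and taken with meals. The first is "a 33% increase in dose over that previously used in a longer (6-month) trial" and the third is "reduced likelihood of any gastrointestinal symptoms". On what participants record at home it says: "Participants will be instructed on storage, rehydration, dosing, and logging of supplement consumption as well as any inadvertent anthocyanin intake". It also mentions interim safety calls, without their number or spacing.

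On adverse events, Safety says "AEs monitored via visits/phone calls (Table 2". On risks it says: "Possible risks are minor including anxiety or fatigue from testing and phlebotomy risks. The possible risks of blueberry consumption are minimal and well-studied".

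Table 2 is not in the public text. Revised Budget cites Table 2 as the place for the budget and its justification. Data Analysis of Outcomes describes summaries of biomarker change and mentions no adverse-event summary. It expects few drop-outs, partly because it regards the intervention as benign.

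**The concern.** Two features of the plan do not fit together well. The symptom used to help justify how the supplement is given is not named where risks are listed. And the stated route for learning about symptoms is contact with staff at intervals, in people chosen because their delayed recall is impaired. The plan already has a home record that could catch symptoms on the day, but it is described only for intake.

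Possible Outcomes says the data should support a larger controlled trial. That trial will need a drop-out allowance and some view of tolerability at this daily amount. With 10 participants, one or two unrecorded reports can turn a visible signal into none, and a clean record would then be read as good tolerability.

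**Working it through.** **Plan's own figure.** The plan gives no gastrointestinal event rate, no capture rate and no derivation of the sample size, so there is no statistical figure to reproduce. The one relevant number is the stated dose increase: 36 / 1.33 = 27.1 g/d for the earlier trial, so the daily amount here is about 9 g/d higher. This only restates the plan's figure.

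**Passages side by side.**
- Dose paragraph: gastrointestinal symptoms are one of three reasons for the regimen.
- Safety: testing and phlebotomy risks are named; product risks get a general sentence with none named.
- Dose paragraph: the home log covers supplement and stray anthocyanin intake; symptoms are not mentioned.
- Safety: the mode of contact is given; how events are elicited is not, and a table is cited that cannot be seen here.

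**What incomplete capture would do.** Inputs: n = 10 (Study Design); p = true 12-week proportion of participants with a reportable gastrointestinal symptom (assumed); s = share of affected participants whose symptom is recorded (assumed). Participants are taken as independent, with no false reports.

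P(at least one recorded) = 1 − (1 − p·s)^10

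| p | s = 100% | s = 80% | s = 50% |
|---|---|---|---|
| 10% | 1 − 0.90^10 = 65.1% | 1 − 0.92^10 = 56.6% | 1 − 0.95^10 = 40.1% |
| 20% | 1 − 0.80^10 = 89.3% | 1 − 0.84^10 = 82.5% | 1 − 0.90^10 = 65.1% |

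**What a clean record would mean.** If 0 of 10 have a recorded symptom, the exact one-sided 95% upper limit for the recorded proportion is 1 − 0.05^(1/10) = 25.9%. Dividing by s gives the limit for the true proportion: 25.9 / 0.8 = 32.4% at 80% capture, and 25.9 / 0.5 = 51.8% at 50%. Even with full capture, zero events exclude little.

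**Using the washout as a comparison.** The washout is 2 weeks and the supplement period 12. Suppose the product has no effect and a constant background gives 20% over 12 weeks. Over 2 weeks the same background gives 1 − 0.8^(2/12) = 3.7%. Among 10 people that is about 0.4 expected in washout against 2.0 on supplement, an apparent excess due only to unequal time. Any such description therefore needs equal windows or rates per participant-week (10 × 2 = 20 against 10 × 12 = 120).

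**The case against.** The strongest reply is that the text gives the mode of contact, not the method of elicitation. Table 2 might hold a call schedule or a symptom checklist. Participants must have near-normal function, dementia is excluded, interim safety calls exist, and a symptom present at the time of a call needs no delayed recall. Because the trial is open, awareness of the product could raise reporting. All of this stands, so only a possibility of under-recording can be claimed. A reader might infer that the pilot is bound to under-count gastrointestinal events; the documents do not show that.

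Three other strong readings also fail.
- A reader might take gastrointestinal symptoms to be the supplement's tolerability limit. They are one of three dose reasons, and the exclusion of gastrointestinal disorders is tied to digestion and absorption.
- A reader might see a contradiction between the general statement on blueberry risks and the 33% increase. Exceeding one earlier trial's amount does not show that the amount is unstudied, and the risk list is worded as open-ended.
- A reader might conclude that participants are not told of the risk. The consent pages are not in the public text, so this cannot be judged.

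It is also fair to say that the plan states no tolerability objective and that the biomarker outcome and its analysis are untouched. That limits the weight of the point but does not remove it: the results are meant to inform a larger trial, and low drop-out is assumed partly on tolerability. A daily record would help even if Table 2 contains a checklist, because it does not depend on memory between contacts.

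**Conclusion.** The point holds as a cheap improvement to adverse-event capture, together with a wording reconciliation. Gastrointestinal symptoms are used in the dose rationale and not named in Safety. Events are gathered at visits and calls from people with impaired delayed recall, and the described home log has no place for symptoms. Mild, transient events may be missed.

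The size is not known. The table above shows that it depends mainly on capture: at 80% the loss in the chance of seeing at least one affected participant is 7 to 9 percentage points, and at 50% it is 24 to 25. Both the 10% to 20% symptom rate and the capture shares are assumptions. The primary aim is unaffected; the consequence is confined to what the pilot can say about tolerability and drop-out.

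**What to change.** 1. Add a brief daily symptom line to the existing home log, with gastrointestinal items plus an open item for anything else, starting on the first day of washout.
2. Have staff go through the log at the safety calls and visits already planned, and state in Safety how events are elicited.
3. Add a descriptive adverse-event summary to Data Analysis of Outcomes: number of participants affected, with exact intervals. If washout and supplement periods are described together, use equal-length windows or rates per participant-week, and note that diet also changes during washout, so it is not a neutral baseline.
4. Reconcile the risk wording in Safety with the dose rationale. This takes no view on the dose.
5. Check the Table 2 reference in Safety, since Revised Budget cites the same table for the budget.

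Cost: one line on a log that participants already keep, and a wording amendment. No visit, assay or participant is added. The downsides are slightly more participant burden and a higher, less favourable event count than unprompted reporting would give.

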Sensitivity of the platform is 100-1000-fold higher than traditional ELISAs and chemiluminescence and electroluminescence (Luminex, Mesoscale) platforms. The instrument is being used for a number of ongoing NIH studies of brain dysfunction and the laboratory staff are fully trained in its use. For each participant, peripheral venous blood are drawn after overnight fasting in EDTA-coated tubes. Within 30 minutes after collection, blood is centrifuged to obtain plasma, aliquoted and stored at -80°C. The concentration of plasma A β 40, A β 42, tau and NFL are measured. Neurology 4-Plex E (included A β 40, A β 42, NFL, GFAP) and pTau181 kits are used according to the kit protocols with minor modifications. To eliminate inter-assay variability as a confounding factor, all samples belonging to the same subject were run in duplicate on the same day with the same standard. The few samples with intra-assay coefficients of variation >20% are measured again. All measurements were performed by professionally trained technicians blinded to participant's state and clinical data. The platform can also measure GFAP (LOD 0.26 pg/ml, range 0-40000 pg/ml).

A list of over 400 publications and posters validating the technology and its utility in neurological disorders can be found here (<https://www.quanterix.com/resources/publications-posters/neurology>).

Analyte	LoD (pg/mL)	LoQ (pg/mL)	Dynamic Range (pg/mL)	Median Endogenous (pg/mL)	Sample Volume (μ L)	Sample Type*
NF-Light	0.072	0.343	0-1,800	7.34	25 μ L	E, S
A β 40	0.196	0.675	0-800	209	25 μ L	E
A β 42	0.045	0.142	0-400	11.1		
Tau	0.019	0.063	0-400	1.43

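### Should the ten-person pilot be required to summarise biomarker change on the log scale rather than in pg/mL?

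*Combined protocol and SAP*

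**What the plan says.** The design is a single-arm "12-week open pilot trial" (Study Design), and the size is stated without derivation: "We will enroll 10 participants with MCI". The Primary Aim is to produce pilot data "in order to calculate sample size estimates for future trials", and Data Analysis of Outcomes repeats the purpose: "As such this is a pilot study designed to generate power estimates for a larger future trial".

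The outcomes are plasma concentrations of NfL, GFAP, Aβ42 and p-tau181, taken once before and once after treatment: "Blood biomarkers (primary outcome) will be measured at zero and 12 weeks" (text after the exclusion criteria). The whole analysis plan is one sentence: "Summary statistics will evaluate the change from baseline to endpoint in biomarker outcomes". It does not say whether the change is absolute, percentage or logarithmic, or whether it is summarised by mean and SD or by median and quartiles.

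Table 1 reports assay performance in pg/mL, with median endogenous values (7.34 for NfL, 11.1 for Aβ42) but no SD, quartiles or skewness for any marker. Its one rule on measurement error is a coefficient of variation: "The few samples with intra-assay coefficients of variation >20% are measured again".

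**The concern.** Read without qualification, change from baseline in a concentration is the week-12 value minus the week-0 value, in pg/mL. The outcomes are positive concentrations, and the assay quality rule is a CV, which suggests error that grows with the level. A participant with twice the baseline would then contribute about twice the change and twice the noise. With ten people aged 55 to 85, one high value could weigh heavily in both the mean change and its SD.

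Those two figures are what the pilot exists to deliver. If the raw scale is the wrong one, the future trial inherits a variance that depends on who happened to enrol, and it may be planned larger than necessary. A log-ratio would weight participants equally and could be compared across markers. Naming it would take a sentence or two and would prevent a choice of scale after the results are seen.

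**Working it through.** **1. What can be reproduced.** The documents give N = 10 and no alpha, power, effect size or SD, so there is no stated calculation to reproduce. Every variability figure below is an assumption.

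**2. Proportional model, pilot of 10.** Assumed: lognormal values, within-person log-SD 0.15 per visit, uniform 15% fall, two-sided 5% paired t-test.

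- Log change has mean ln 0.85 = −0.1625 and SD 0.15 × √2 = 0.2121, a standardised effect of 0.766. With ten pairs the power is 58%.
- Raw change was simulated (40,000 pilots per row). The planning-N ratio is (log standardised effect ÷ raw standardised effect)².

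| Between-person CV | Power, log | Power, raw | Planning N, raw ÷ log | Median pilot raw SD ÷ true raw SD |
|---|---|---|---|---|
| 30% | 58% | 54% | 1.17 | 0.93 |
| 50% | 58% | 49% | 1.4 | 0.88 |
| 70% | 58% | 43% | 1.8 | 0.81 |

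Under this model raw change is less efficient. The last column shows that a typical pilot does not pass on an inflated raw SD: the sample SD falls below its true value in 60% to 69% of pilots.

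**3. Proportional model, future two-arm trial.** Assumed: NfL median 7.34 pg/mL (Table 1), 20% reduction, two-sided 5%, 80% power, 1:1 allocation. Per arm, n = 2(1.960 + 0.842)² × SD² ÷ δ² = 2 × 7.849 × SD² ÷ δ².

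- Log, within-person log-SD 0.15: SD² = 2 × 0.15² = 0.045 and δ² = (ln 0.8)² = 0.0498, so n = 14.2, rounded up to 15. Raw: 17 to 32 as the between-person log-SD goes from 0.1 to 0.7.
- Log, within-person log-SD 0.25: SD² = 0.125, so n = 39.4, rounded up to 40. Raw: 47 to 81.

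The ratio runs from about 1.1 to 2.1. On average the highest-baseline person supplies 22% to 36% of the squared deviations in raw change, against 10% to 17% on the log scale. That is disproportionate but still a minority share.

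**4. Additive model.** Keep the same spread of baselines but make error and effect constant in pg/mL.

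- Future trial, SD 1 per visit and a fall of 1: raw n = 2 × 7.849 × 2 ÷ 1 = 31.4, rounded up to 32 per arm. Log needs 35 (between-person log-SD 0.3) or 43 (0.5).
- Pilot of 10, SD 0.8 per visit and a fall of 1.1: the raw standardised effect is 1.1 ÷ (0.8 × √2) = 0.972, giving power of about 78%. Log power is about 73%, 65% and 58% at between-person CV 30%, 50% and 70%. Pilots with a value at or below 0.2 pg/mL were left out (up to 12% of them at CV 70%).

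The ranking reverses, so the direction depends on the error model and not only on the spread between people.

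**5. What the CV rule establishes.** It concerns duplicate readings of a sample in the assay. It says nothing about whether a person's biological variation over 12 weeks, or any effect of the supplement, scales with concentration.

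**6. Precision from ten people.** For normal data with 9 degrees of freedom, the 95% interval for the SD is 0.688 to 1.826 times the estimate. Squared, the interval for the variance, and hence for the planning N at a fixed effect, is 0.47 to 3.33 times the estimate.

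**The case for a change.** The strongest case for a change is that the SD of change is the pilot's main product, so the plan should say on which scale it will be computed. Proportional variation is a reasonable working assumption for positive concentrations. Under it the raw SD is also less stable: its relative spread between pilots is 0.25 to 0.55 across the settings in step 3, against 0.24 for the log SD. A raw SD that is usually too low and occasionally very high is a poor planning input, and the imprecision of ten people is a reason not to lose more.

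Part of this stands. The scale and the summary statistic are not written down, and a log-ratio reported beside raw changes and individual paired plots would be a sensible presentation. The rest does not amount to a fault in the plan. The text does not commit the analyst to pg/mL differences. A raw SD used with an effect on the same scale is a valid planning input, even where it is less efficient. The power comparisons describe a paired test that the protocol does not contain. Choosing the scale after seeing the data has limited consequence here, because no claim of success or failure hangs on it, and whoever designs the future trial can work from the same ten pairs on any scale.

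**Conclusion.** No change to the plan is needed. The raw-scale reading is inferred from silence, and the CV rule cannot support a claim about 12-week change within a person. The preference for log change holds under proportional variation (raw planning N about 1.2 to 1.8 times larger for an assumed between-person CV of 30% to 70%, and 1.1 to 2.1 across the wider grid). It reverses under additive variation (32 per arm raw against 35 to 43 log). The documents give no spread for any marker, so they do not settle which applies.

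What remains is missing detail that a competent analyst will supply by summarising the ten pairs on the scale the next trial intends to use. On either scale the uncertainty from n = 10, a factor of 0.47 to 3.33 in planning N for normal data, is larger than the effect of the choice. The conclusion assumes that the individual week-0 and week-12 values are kept and that the pilot stays descriptive, as the plan says.
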